3. TRIAL DESIGN

This is a Phase IV, multicenter, double-blind, randomized, placebo-controlled trial to measure visual field sensitivity in subjects with partial epilepsy dosed with pregabalin or placebo. Pregabalin will be dosed at 300 mg/day for 11 weeks after one-week initiation with 150 mg/day, followed by one-week tapering of 150 mg/day. Total treatment period will be 13 weeks. Comprehensive ophthalmologic testing will be done at pre-treatment baseline to exclude subjects with pre-existing eye disease.

A central reader will assure the quality of all visual field test results with pre-specified criteria. Any field failing this quality assurance criteria either due to poor subject compliance or due to failure to follow testing procedures will be repeated as soon as possible within 2 weeks following notification from the central reader. Prior to randomization subjects must

meet the pre-specified quality assurance criteria. Subjects failing to meet this criteria at Baseline either due to poor subject compliance or due to failure to follow testing procedures can be re-screened one additional time after 3 months and will keep their previously assigned ID number. Rescreening may also be allowed for subjects with non-lesional epilepsy who may have been screen failed for reasons other than those specified above, if correctable.

Approximately 187 subjects will participate in the study. Subjects will be randomized 1:1 to pregabalin or placebo, with approximately 93 randomized to pregabalin and 93 to placebo.

4. SUBJECT SELECTION

This clinical trial can fulfill its objectives only if appropriate subjects are enrolled. The following eligibility criteria are designed to select subjects for whom protocol treatment is considered appropriate. All relevant medical and non-medical conditions should be taken into consideration when deciding whether this protocol is suitable for a particular subject.

4.1. Inclusion Criteria

Subjects must meet the following criteria to be eligible to participate in the study:

1. Diagnosis of epilepsy with partial seizures (as defined in the International League Against Epilepsy Classification of Seizures). Diagnosis must be established by subject's medical history (eg, seizures), family history, and the results of electroencephalogram testing done within 2 years prior to baseline (if none available, must be taken during Screening). Results must be consistent with the diagnosis of focal-onset epilepsy;
2. Seizures should not have occurred within 2 weeks of an acute neurological event (eg, a stroke);
3. Be currently taking 1 to 3 antiepileptic drugs (AEDs). Vagus nerve stimulator (VNS) device also will be considered an AED. AED should be continued without alteration of current dose during the study. Benzodiazepines and barbiturates will not be allowed as treatment regardless of indication;
4. Have magnetic resonance imaging (MRI) or computed tomography (CT) scan **with contrast** of the head within 3 years prior to randomization (if none available, must be taken during Screening) that demonstrates no progressive structural abnormality and non-lesional epilepsy;
5. Subjects who, in the opinion of the investigator, may benefit from treatment with pregabalin;
6. Be 18 to 65 years old;

7. Be male, or nonpregnant, nonlactating female who is postmenopausal, surgically sterilized, or premenopausal using a reliable method of contraception (including barrier or hormonal method) and have a confirmed negative urine pregnancy test prior to randomization;
8. Have a 12-lead electrocardiogram prior to randomization without clinically significant abnormal findings;
9. On both screening and baseline visual field exam, any eye has <20% false positives, <30% false negatives, <30% fixation loss;
10. Difference in mean deviation between screening and baseline visual field exams must be ≤ 2 decibels (dB) of mean deviation (MD) on both eyes;
11. Provide written informed consent signed by subject or legal guardian prior to entering the study;
12. Subjects who are willing and able to comply with scheduled visits, treatment plan, laboratory tests, and other trial procedures.

4.2. Exclusion Criteria

Subjects may **not** participate in the study if they meet any of the following criteria:

- Known previous or current serious ophthalmologic disease (including uncorrected cataracts or history of cataract surgery <8 days), serious eye trauma or intra ocular or ocular surgery other than refractive (ie, lasik, cataract) surgery, or ophthalmologic finding that could affect the visual field;
- Amblyopia;
- Ptosis;
- Manifest nystagmus in primary gaze;
- On medications that could affect the visual field or pupil eg, chloroquine or miotics;
- Refractive error in either eye exceeding ± 5 D (sphere) or ± 2.5 D (cylinder);
- Best corrected Early Treatment Diabetic Retinopathy Study (ETDRS) visual acuity worse than 20/25 in either eye;
- Intra ocular pressure (IOP) >22 mmHg in either eye at Screening;

- Have clinically significant abnormal findings on ophthalmologic examinations including external eye examination, visual acuity test, intraocular pressure, funduscopy and repeated visual field test (VFT). Repeat any test if there is a finding that is uncertain. For VFT – if one test is normal and another one abnormal a third test may be performed. Two of the three tests being normal is acceptable;
- Subjects with glaucoma or a history of glaucoma;
- Family history of inherited retinal or optic nerve disorders;
- Subject with a history of intolerability to pregabalin, or with a history of insufficient response (based on investigator’s clinical judgment) to pregabalin in the treatment of partial seizure, or subjects with current pregabalin treatment;
- Subjects who currently have poorly controlled epileptic seizures which could interfere with test procedures;
- Childbearing potential female who is unable to take adequate contraceptive precautions, has a positive pregnancy test result within 24 hours prior to study entry, is otherwise known to be pregnant, plans to become pregnant in the next 3 months or is currently breastfeeding an infant;
- Creatinine clearance ≤ 60 mL/min (estimated from serum creatinine);
- Have a history or clinical evidence of cardiovascular, hematologic, hepatic, or renal disease (ALT, AST, bilirubin, urea, or creatinine values above twice the upper limit of normal [ULN] at Screening) or any physical conditions that, in the opinion of the investigator, would compromise participation in the study;
- With a mental condition rendering the subject unable to be cooperative with and complete study requirements;
- Have a significant psychiatric disorder, recurrent episodes of severe depression (any pharmacologic treatment or hospitalization for the illness within 1 year prior to Screening), or subjects with serious suicidal risk per criteria described in the [Section 7.5.1](#) of the protocol. Subjects with mild, chronic depression without recent hospitalization who are being maintained on a stable dose of a single antidepressant are acceptable;
- Has received any investigational drug during the previous 60 days prior to first dose;
- Hypersensitivity to pregabalin or gabapentin;
- Meets criteria for alcohol or drug abuse within the past year;

- Other severe acute or chronic medical or psychiatric condition or laboratory abnormality that may increase the risk associated with trial participation or investigational product administration or may interfere with the interpretation of trial results and, in the judgment of the investigator, would make the subject inappropriate for entry into this trial;
- Any subject at risk of suicide or self harm based on investigator judgment and/or details of a mental health risk assessment (MHRA) by a qualified mental health professional, as specified in [Section 7.5](#).

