This is a Phase IV, multicenter, randomized placebo-controlled trial to further characterize visual fields in subjects with partial epilepsy dosed for 13 weeks, including a 1 week up titration and 1 week down titration from the target dose of pregabalin 300 mg/day versus placebo. Comprehensive ophthalmologic testing will be done at pre-treatment baseline to exclude those with pre-existing eye disease.

Approximately 187 subjects will participate in the study. Subjects will be randomized 1:1 to pregabalin or placebo, with approximately 93 randomized to pregabalin and 93 to placebo.

Endpoints:

The primary endpoint is the proportion of subjects with a decrease in the threshold value from baseline to termination in five or more points (in either eye) at the $p < .05$ level repeated in the same five points on subsequent computerized automated perimetry testing (Humphrey 24-2 SITA standard).

Trial Treatments:

Subjects will receive oral pregabalin 75 mg twice daily (BID) (150 mg/day) or matching placebo for titration and taper. Subjects will receive oral pregabalin 150 mg BID (300 mg/day) or matching placebo for the treatment phase.

Statistical Methods:

The primary endpoint will be analyzed using a non-inferiority analysis. The difference in proportions between pregabalin and placebo in the per protocol population will be compared using a 2-sided 95% confidence interval (CI). Non-inferiority will be demonstrated if the upper CI bound is less than 0.10 (10%). The proposed sample size will have >90% power to detect non-inferiority on the primary endpoint, assuming a proportion of 1% for each group.

SCHEDULE OF ACTIVITIES

Protocol Activity	Screening	Baseline	Wk 0 Randomization	Wk 1	Wk 6	Wk 12 (Or ET)	Week 15 (Follow-Up)
Visit Number ⁿ	1	2	3 ^m	4	5	6	7
Informed Consent	X						
Inclusion/Exclusion Criteria	X	X	X				
Review/document contraception use	X						
History/Diagnosis/Demographics	X						
Physical Examination ^p	X					X	
Concomitant Medication	X	X	X	X	X	X	X
Body Weight	X	X		X	X	X	X
Vital Signs (Sitting BP/HR)	X	X		X	X	X	
ECG (Singlet)	X						
EEG	X ^a						
CT or MRI	X ^b						
Clinical	1) Hematology ^c	X				X	
Laboratory	2) Chemistry ^d	X				X	
	3) Urinalysis ^e	X				X	
Urine Pregnancy Test ^f	X					X	
Urine Drug Screen	X						
Ophthalmic Examination	1) External Eye Exam	X				X	X ^g
	2) ETDRS Acuity	X	X		X	X	X ^g
	3) Intraocular Pressure	X					
	4) Dilated Funduscopic	X					
	5) VFT (24-2 SITA)	X ^{h,i}	X ^{h,i}			X ^h	X ^h

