Patient assessment of seizure frequency						X	

Protocol Activity	Screening	Baseline	Wk 0 Randomization	Wk 1	Wk 6	Wk 12 (Or ET)	Week 15 (Follow-Up)
Investigational product Dispensing			X ^{i,j}	X ^k	X ^k	X ^j	
Dispense Dosing Diary			X		X		
Review Dosing Diary with subject				X	X	X	X
Sheehan-Suicidality Tracking Scale (S-STSS) ^{o,r}	X	X	X	X	X	X	X
Columbia-Suicide Severity Rating Scale (C-SSRS) ^{o,r}	X	X	X	X	X	X	X
Suicidal Behaviors Questionnaire – Revised (SBQ-R) ^r	X						
Patient Health Questionnaire–8 (PHQ-8)	X						
Assessment of need to complete a risk assessment ^q	X	X	X	X	X	X	X
Adverse Events Report			X			X	

- a. Subjects who have not had a test within 2 years. See inclusion criteria 1.
- b. Subjects who have not had a test within 3 years. See inclusion criteria 4.
- c. Hemoglobin, hematocrit, RBC count, WBC count, platelet count.
- d. Electrolytes (Na, K, Ca, Cl, bicarbonate), creatinine, BUN, glucose, AST, ALT, alkaline phosphatase, bilirubin, CK, uric acid, albumin, total protein.
- e. Specific gravity, PH, Glucose (qual), Protein (qual), Blood (qual), Ketones, Nitrite and Microscopy if urine dipstick is positive for blood or protein.
- f. Childbearing potential female subjects only.
- g. Subjects who have had visual findings on Week 12 and subsequently confirmed.
- h. A repeat may be necessary upon the confirmation from central reader.
- i. Recommend subject to take first dose in the evening.
- j. Titration/tapering dose.
- k. Treatment dose.
- l. Conduct 2 tests.
- m. Usually occur between the 3rd – 7th day after Baseline (Visit 2) when the verification of VFT is available.
- n. Screening procedures can be completed within 21 days prior to Baseline; Study Visits 4 – 7 have a ±3 days window.
- o. The “Lifetime” assessment is completed at Screening and the “Since Last Visit” assessment is completed at **all** other visits.
- p. Including neurological exam at screening.
- q. A risk assessment must be performed and documented if the subject meets the criteria detailed in Protocol.
- r. Subjects screened/randomized under Amendment 3 will continue the S-STSS for assessment of suicidal ideation and behaviour. Subjects screened /randomized under Amendment 4 will have suicidal ideation and behaviour assessed by the C-SSRS and the SBQ-R.

TABLE OF CONTENTS

SCHEDULE OF ACTIVITIES.....	7
LIST OF TABLES	12
APPENDICES	12
1. INTRODUCTION	13
1.1. Background	13
1.2. Rationale.....	14
2. TRIAL OBJECTIVES AND ENDPOINTS	14
2.1. Objective	14

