6. TRIAL PROCEDURES

6.1. Screening

At the Screening Visit (up to 21 days prior to Baseline), subjects will be eligible for the study after verification of the inclusion/exclusion criteria and the study has been explained to them. The following procedures will be completed at the screening visit:

- Obtain written informed consent (must be signed prior to the initiation of any study related activities);
- Verify inclusion/exclusion criteria;
- Record demographic information, medical history, and diagnosis;
- Record concomitant medications;
- Perform physical exam including neurologic exam;
- Collect vital signs (sitting blood pressure, heart rate);
- Perform electrocardiograph;
- Prescribe/perform EEG, CT and MRI if necessary (inclusion criteria 1 and 4);
- Collect body weight;
- Collect blood samples for clinical laboratories;
- Blood chemistry;
- Hematology;
- Urinalysis including drug screen;
- Urine pregnancy test (females of child-bearing-potential);
- Columbia-Suicide Severity Rating Scale (C-SSRS) Lifetime Assessment;
- Suicide Behaviors Questionnaire-Revised (SBQ-R);

- Patient Health Questionnaire – 8 (PHQ-8);
- Determine if mental health risk assessment (MHRA) is required (refer to [Section 7.5](#));
- Ophthalmic Examination.
 1. External eye examinations.
 2. Best corrected ETDRS visual acuity.
 3. Intraocular pressure to be measured by a calibrated applanation tonometer such as Goldmann, Perkins, or Tonopen.[®] If more than one tonometer is available at the site, the same one should be used consistently throughout the study.
 4. Computerized automated perimetry (Humphrey 24-2 SITA standard) 2 times on both eyes with a minimum 5 minute break between each eye tested and minimum 10 minutes (may take longer break if needed) between 2 tests.
 5. Dilated fundoscopic examination. Recommend subject to wear sunglasses for at least one hour after this procedure and to bring someone along for driving home.

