6.2.2. Randomization (Week 0) Visit

At this visit, subjects will be randomized after verification that they continue to meet the inclusion/exclusion criteria. This visit occurs after the central reader confirms the validity of the VFTs, ie, usually between 3 and 7 days after the Baseline visit.

The following procedures will be completed prior to randomization:

- Verify inclusion/exclusion criteria;
- Confirmation from Central Reader that VFTs are valid and useable prior to dosing;
- Concomitant medications;
- Adverse events;
- Complete C-SSRS Since Last Visit assessment (or C-SSRS Lifetime assessment if not completed at prior visit);
- Complete SBQ-R if not completed at a prior visit;
- Determine if MHRA is required based on results of screening and subsequent assessments of suicidal ideation and behavior. No subject can be randomized until a risk assessment has been completed and documents eligibility to participate in the study in applicable subjects (refer to [Section 7.5.5](#)).
- Dispense investigational product (titration dose). Recommend subject take the first dose that evening.
- Provide dosing diary and instructions for use to the subject.

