7.2. Clinical Laboratory Tests

Laboratory

The following safety laboratory tests will be performed at the Screening (Visit 1) and Week 12 (Visit 6).

Safety Laboratory

Hematology	Chemistry	Urinalysis	Other
Hemoglobin	Creatinine	PH	Urine Pregnancy test ^a
Hematocrit	BUN	Color	Urine drug testing ^c
RBC Count	Glucose	Clarity	(amphetamines,
Platelet Count	Ca ⁺⁺	Specific gravity	antidepressants,
WBC Count	Na ⁺ , K ⁺ , Cl ⁻	Glucose (qual)	barbiturates,
	Total CO ₂	Protein (qual)	benzodiazepines,
	(Bicarbonate)	Blood (qual)	canabinoids, cocaine,
	AST, ALT	Ketones	methadone,
	Total Bilirubin	Nitrites	methaqualone,
	Alkaline phosphatase	Microscopy ^b	opiates,
	Uric acid		phenothiazines,
	Albumin		propoxyphene and
	Total protein		alcohol)
	Creatine phosphokinase		

^a Childbearing potential females only.
^b Only if urine dipstick is positive for blood or protein.
^c Only at Screening.

Results of the urine drug tests at screening (V1) must be negative for the subject to receive trial medication on Day 1.

- Safety laboratory tests from Screening must have no clinically significant findings, as judged by the investigator, in order for a subject to receive trial medication on Day 1.
- CL_{cr} (must be >60 ml/min) will be estimated from serum creatinine at screening to determine eligibility using the equations that follow.¹³

$$\text{Male } \text{CL}_{\text{cr}} = \frac{(140 - \text{age}) \times \text{Body Weight (kg)}}{72 \times \text{Serum Creatinine}}$$

$$\text{Female } \text{CL}_{\text{cr}} = \left[\frac{(140 - \text{age}) \times \text{Body Weight (kg)}}{72 \times \text{Serum Creatinine}} \right] \times 0.85$$

In order to use SI units for creatinine ($\mu\text{mol/L}$), use the following formulas:

$$\text{Male } \text{CL}_{\text{cr}} \text{ (mL/min)} = \frac{(140 - \text{age}) \times \text{Body Weight (kg)}}{\text{Serum Creatinine}} \times 1.23$$
$$\text{Female } \text{CL}_{\text{cr}} \text{ (mL/min)} = \left[\frac{(140 - \text{age}) \times \text{Body Weight (kg)}}{\text{Serum Creatinine}} \right] \times 1.23 \times 0.85$$

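### The only scheduled pregnancy test before dosing is at Screening, up to 28 days before the first dose on the usual path, and the 24-hour exclusion is tied to an undefined study entry

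*Protocol*

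**What the plan says.** Two eligibility criteria in the Protocol deal with pregnancy status. Inclusion 7 (4.1) asks for a negative urine test at some time before randomisation and sets no limit on its age. The exclusion in 4.2 covers a woman who "has a positive pregnancy test result within 24 hours prior to study entry", along with women known to be pregnant by other means, planning pregnancy in the next 3 months, or unable to use adequate contraception.

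Tests are scheduled at two points only. Section 6.1 lists "Urine pregnancy test (females of child-bearing-potential") at Screening, and 6.2.4.2 lists it again at Week 12. Section 7.2, whose table includes the urine pregnancy test, says: "The following safety laboratory tests will be performed at the Screening (Visit 1) and Week 12 (Visit 6"). The Schedule of Activities agrees. The procedure lists for Baseline (6.2.1), Randomization (6.2.2), Week 1 (6.2.3) and Week 6 (6.2.4.1) contain no pregnancy test. The Schedule row "Review/document contraception use" is marked at Screening only.

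On timing, footnote n to the Schedule says "Screening procedures can be completed within 21 days prior to Baseline" and that Visits 4 to 7 "have a ±3 days window". Section 6.2.2 puts randomisation "usually between 3 and 7 days after the Baseline visit", with the first dose recommended that evening. It also says "subjects will be randomized after verification that they continue to meet the inclusion/exclusion criteria".

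**The concern.** A 24-hour window suggests that pregnancy is ruled out immediately before exposure. The schedule does not deliver this. The only test before dosing may be weeks old, and the event that anchors the 24 hours is not defined, although neighbouring criteria name theirs (randomisation in Inclusion 4, 7 and 8; first dose in the exclusion for recent investigational drugs).

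What is at stake is fetal exposure to the study drug, not the primary or secondary analyses. A pregnancy that begins after Screening and is not recognised by the woman would pass every scheduled check before dispensing. Section 8.10 treats exposure during pregnancy as reportable within 24 hours on an SAE form even when no SAE has occurred, so avoidable exposure is something the plan should try to prevent.

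**Working it through.** The plan states no test-to-dose interval, so there is no figure to reproduce. The intervals follow from its own visit windows.

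**Inputs**
- Screening to Baseline: at most 21 days (6.1; Schedule footnote n).
- Baseline to randomisation: usually 3 to 7 days (6.2.2; footnote m).
- Randomisation to first dose: same evening, counted as 0 days (6.2.2; 5.4.3).
- Randomisation to Week 12: 12 × 7 = 84 days, ±3 days (6.2.4; footnote n).
- Repeat of a poor-quality field: up to 14 days after notification (Section 3; 7.1.4).
- Central read: 3 working days (7.1.4), taken here as 3 to 5 calendar days. This conversion is an assumption.

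**Age of the Screening test at first dose, usual path, full screening window**
- 21 + 3 + 0 = 24 days to 21 + 7 + 0 = 28 days.
- If Screening and Baseline fell on the same day (assumption), the gap would be only 3 to 7 days. The 28 days is a maximum, not a typical value.

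**The same gap if a baseline field is repeated** (read, full repeat window, second read)
- 21 + 3 + 14 + 3 = 41 days to 21 + 5 + 14 + 5 = 45 days.

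**First dose to next scheduled test, for a woman who stays on treatment**
- 84 − 3 = 81 days to 84 + 3 = 87 days. A woman who withdraws early is due a test at that visit (6.4).

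**Longest interval between two scheduled tests**
- Usual path: 24 + 81 = 105 days to 28 + 87 = 115 days.
- With a repeat: 41 + 81 = 122 days to 45 + 87 = 132 days.

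**What the 24-hour exclusion can do**
- If study entry means randomisation or first dose, no scheduled test falls inside the 24 hours, so the criterion has no result to act on.
- If study entry means Screening, the Screening test fits the window, but the criterion then says nothing about pregnancy status 24 to 28 days later.

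**What the other eligibility text can do**
- Inclusion 7 is met by the Screening test whatever its age.
- The eligibility check at Visit 3 has no current pregnancy result behind it. The same visit does collect a fresh C-SSRS, so current information is obtained there for suicidality but not for pregnancy.

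**The case against.** The strongest reply is that study entry can be inferred. Consent is required before a subject enters the study (Inclusion 11) and is taken at Screening. Section 7.3 compares later findings with an entry examination, and the only physical examination before dosing is at Screening. On that reading the exclusion matches the Screening test and the documents do not contradict each other. Section 7.2 also uses the Screening laboratory results and drug screen as the condition for Day 1 dosing, so Screening looks like a deliberate gate. This reading is plausible. It removes the contradiction, but the old test at dosing remains.

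Second, there are real safeguards. Inclusion 7 requires a nonpregnant woman using reliable contraception, and this is verified again at Baseline and Randomization. Section 4.4 adds counselling and an instruction to call at once if pregnancy is suspected. These lower the risk, but none of them detects an unrecognised pregnancy. The rule for highly effective contraception in 4.4 is worded for the active treatment period and at least 28 days after the last dose, so it does not expressly cover the interval from Screening to dosing.

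Third, the repeat-path figures are worst cases. They combine the full screening window with the full repeat window, although repeats are due as soon as possible. Appendix 2 gives 72 hours for the central reader's response, which favours the lower end, and Section 3 and 6.2.1 also offer rescreening after 3 months to subjects who fail at Baseline. This is fair, and the conclusion does not depend on those figures.

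Fourth, the reach may be small. Protocol 9.1 in Amendment 5 speaks of 187 enrolled subjects, while the Document History says enrolment is to be approximately 187. How many women remained to be randomised cannot be told from the documents.

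**Conclusion.** The concern holds. Four places in the Protocol agree that the only scheduled pregnancy test before dosing is at Screening. The plan's own windows allow it to be up to 24 to 28 days old at the first dose on the usual path, and about 41 to 45 days if a baseline field is repeated, the latter resting on the assumed 3 to 5 calendar days per read. Neither reading of study entry closes the gap. After dosing, the next scheduled test comes at 81 to 87 days, or at early termination.

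The probability of an exposed pregnancy cannot be estimated, because the documents give neither the share of women of childbearing potential nor a conception rate. Sites may retest on their own initiative, but the plan does not require it. The change should be made on safety grounds; it has no bearing on power, error rates or the estimates.

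**What to change.** - Add a urine pregnancy test for women of childbearing potential at the Randomization visit (Visit 3), with a negative result required before dispensing. Keep the Screening test. Enter the new test in the Schedule row, in 6.2.2 and in 7.2, and carry it into the copy of the Schedule in SAP 2.1.
- In 4.2, replace *study entry* with *randomization*.
- Align Inclusion 7, for example: *have a negative urine pregnancy test at Screening and again within 24 hours prior to randomization*.

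The gap between the last test and the recommended first dose then falls from a maximum of 24 to 28 days to the same day. The cost is one dipstick per woman of childbearing potential at a visit that already takes place. That is at most about 187 tests even if every subject in the planned total were such a woman, so the true number is lower. Visit dates, blinding and endpoints do not change. Only women not yet randomised benefit.
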